### 3.3. Study Definitions and Defined Variables

The baseline value will be defined as the last value obtained prior to the first vaccination. Individual antibody endpoint titers will be reported with values of  $C^*2^k$ , where  $k=0, 1, 2, \dots$

and C may vary depending on the dilutions used for a given assay. Values below each assay's limit of detection will be imputed as one-half the limit of detection. For analysis, the geometric mean of replicates for each sample will be computed and used as the response for all subsequent calculations, where applicable.

Immune response over time will be assessed by the positive incremental area under the curve (AUC) based on a graph with the analysis value (e.g., log endpoint titer) on the y-axis and visit week on the x-axis.

## 4. INVESTIGATIONAL PLAN

### 4.1. Overall Study Design and Plan

This is a phase I randomized, double-blind clinical trial to optimize ALFQ dosing among healthy adults not living with HIV. A total of 60 participants will be enrolled to one of three arms (N=20 in each arm) with each arm receiving 300 micrograms of A244 and B.63521. In addition, arm 1 will receive 200 micrograms of ALFQ, arm 2 will receive 100 micrograms of ALFQ, and arm 3 will receive 50 micrograms of ALFQ. The safety, reactogenicity, and immunogenicity will then be compared among the three arms to determine the optimal dose of ALFQ.

All vaccinations will be split into 2 half doses which will both be administered intramuscularly (IM) into the same deltoid muscle. Vaccinations will occur at months 0, 1, and 2. The second vaccination will be administered into the contralateral deltoid at study month 1 compared to the first vaccination at study month 0. The third vaccination at study month 2 will be administered into the same deltoid as the first vaccination at study month 0. Participants will be followed for 12 months following the last study vaccination. Table S2 provides a schematic for the study design.

**Table S2:** Study Design

Number of participants (N) = 60		Vaccination schedule in months (days)		
	Number of participants (N)	Month 0 (Day 1)	Month 1 (Day 29)	Month 2 (Day 57)
Arm 1	20	300µg A244	300µg A244	300µg A244
		300µg B.63521	300µg B.63521	300µg B.63521
		200µg ALFQ	200µg ALFQ	200µg ALFQ
Arm 2	20	300µg A244	300µg A244	300µg A244
		300µg B.63521	300µg B.63521	300µg B.63521
		100µg ALFQ	100µg ALFQ	100 µg ALFQ
Arm 3	20	300µg A244	300µg A244	300µg A244
		300µg B.63521	300µg B.63521	300µg B.63521
		50µg ALFQ	50µg ALFQ	50µg ALFQ

The schedule of events is given in Table S3 below, for reference

Table S3: Schedule of Events (SOE)

Visit Number	0	1	2	3	4	5	6	7	8	9	10  /Exit 4	Phone Follow-up #1	Phone Follow-up #2
Visit Type	Screen	V1	Safety & Immun	V2	Safety & Immun	V3	Safety & Immun	MAAE follow-up	MAAE follow-up				
Visit Day	-30 to -3	1	15	29	43	57	58-59	64	71	169	337	365	393
Window			± 3d	± 7d	± 3d	± 7d	± 3d	± 3d	± 3d	± 7d	± 7d	± 7d	± 7d
Visit Week	0	2	4	6	8	8	9	9	10	24	48	52	56
Clinical													
Briefing and Contact Information	X												
Informed Consent	X												
Test of Understanding	X												
Enrollment and Randomization	X												
Vaccination	X			X		X							
Vital Signs and Physical Exam 	X	X	X	X	X	X	X	X	X	X	X	X	X
Medical History & Concomitant Medications	X	X	X	X	X	X	X	X	X	X	X	X	X
Adverse Event Documentation (AE, SAE, AESD)	X	X	X	X	X	X	X	X	X	X	X	X	X

Statistical Analysis Plan – RVV575  
Version 2.1

22 January 2024

Visit Number	0	1	2	3	4	5	6	7	8	9	10  /Exit 4	Phone Follow-up #1	Phone Follow-up #2
Visit Type	Screen	V1	Safety & Immun	V2	Safety & Immun	V3	Safety & Immun	MAAE follow-up	MAAE follow-up				
Visit Day	-30 to -3	1	15	29	43	57	58-59	64	71	169	337	365	393
Window			± 3d	± 7d	± 3d	± 7d		± 3d	± 3d	± 7d	± 7d	± 7d	± 7d
Visit Week	0	2	4	6	8	8	9	9	10	24	48	52	56
Medically Attended Adverse Event (MAAE) Documentation 	X	X	X	X	X	X	X	X	X	X	X	X	X
Diary Card	X	X	X	X	X	X	X	X	X	X	X		
HIV Risk Counseling	X	X	X	X	X	X							
Pregnancy Test  & Pre/Post Counseling	X	X	X										
CBC w/ diff	4	4	4	4	4	4				4	4		
Creatinine, ALT	4	4	4	4	4	4				4	4		
Hepatitis B and Hepatitis C Serology	7												
HIV Testing	7		7		7				7	7	7		
Research 													
HIV Binding Antibody		SP	SP	SP	SP	SP	SP	SP	SP	SP	SP		

Visit Number	0	1	2	3	4	5	6	7	8	9	10/Exit 4	Phone Follow-up #1	Phone Follow-up #2
Visit Type	Screen	V1	Safety & Immun	V2	Safety & Immun	V3	Safety & Immun	MAAE follow-up	MAAE follow-up				
Visit Day	-30 to -3	1	15	29	43	57	58-59	64	71	169	337	365	393
Window			± 3d	± 7d	± 3d	± 7d		± 3d	± 3d	± 7d	± 7d	± 7d	± 7d
Visit Week	0	2	4	6	8	8	9	9	10	24	48	52	56
HIV Neutralizing Antibody Assays	6	6	6	6	6	6				6	6		
Functional Antibody Assays	SP	SP	SP	SP	SP	SP				SP	SP		
B-Cell Analysis	17	17	17	17	17	17				17	17	17	17
Multiparameter Flow Cytometry	17	17	17	17	17	17				17	17	17	17
Inmate Cell Analysis	17	17	17	17	17	17				17	17	17	17
Transcriptomics	2.7	2.7	2.7	2.7	2.7	2.7				2.7	2.7		
Additional Immunogenicity Testing	42.5	8.5	8.5	8.5	8.5	8.5				25.5	34	34	
Daily Volume (mL) b	22	110.2	83.2	59.2	83.2	59.2	19.7	19.7	70.7	100.2	98	106	
Cumulative Volume (mL)	22	132.2	215.4	274.6	357.8	417	436.7	507.4	607.6	705.6	811.6		

## Statistical Analysis Plan – RV575

Version 2.1

22 January 2024

Visit Number	0	1	2	3	4	5	6	7	8	9	10  /Exit 4	Phone Follow-up #1	Phone Follow-up #2
Visit Type	Screen	V1	Safety & Immun	V2	Safety & Immun	V3	Safety & Immun	MAAE follow-up	MAAE follow-up				
Visit Day	-30 to -3	1	15	29	43	57	58-59	64	71	169	337	365	393
Window			± 3d	± 7d	± 3d	± 7d		± 3d	± 3d	± 7d	± 7d	± 7d	± 7d
Visit Week		0	2	4	6	8	8	9	10	24	48	52	56
8-Week Cumulative Volume (mL)						395	414.7	375.2	475.4	98	106		

SP = Assay performed from stored plasma; no additional blood volume required

 Full physical examination at screening visit (S1) and targeted physical examination at all other visits. Vitals to be collected both pre- and at about 30 minutes post-vaccination at Visit Day 1, 29, and 57.

 Participants will be contacted for the unblinding visit after the clinical data is locked.

Medically Attended Adverse Events will be followed through the end of the study; a full 12 months following the last vaccination. After clinic visits end, follow-up for MAAEs will occur by monthly phone calls for two months.

For those participants who are unable to continue participation in the study, but who do not withdraw consent, an exit visit will be conducted.

 Research labs may be performed at any visit where sufficient stored samples are available

 Blood volumes for clinical lab assays may be adjusted as long as maximum daily blood volume is not exceeded.

 Pregnancy tests can be conducted at any visit if clinically indicated.

 Any clinically indicated safety labs can be obtained at investigator discretion

## 4.2. Discussion of Study Design

This study design is a randomized, double-blind study, with three study arms of equal allocation (1:1:1) to assess the safety, tolerability, and immunogenicity of ranging doses of candidate vaccine A244/B.63521 with ALFQ adjuvant.

## 4.3. Selection of Study Population

The study population will consist of 60 healthy adults not living with HIV randomized to receive active vaccine with varying levels of ALFQ adjuvant. All study participants must meet the eligibility criteria enumerated in the protocol (protocol version 1.0, sections 5.3.1, 5.3.2).

### 4.3.1. Sentinel Group

As this is a first-in human study, a sentinel group will first be enrolled to conform to the FDA suggestion in order to assess for safety and tolerability in a subset of participants prior to enrolling all 60 participants for the study. A total of six participants will comprise a sentinel group. Four participants will be randomized to the 200 mcg ALFQ group (Arm 1), one participant will be randomized to the 100 mcg ALFQ group (Arm 2), and one participant will be randomized to the 50 mcg ALFQ group (Arm 3), so the blinding is preserved. Safety data per diary card for seven days following vaccination number one will be reviewed by a PSRT. If it is determined to be necessary by the PSRT, the MHRP Safety Monitoring Committee (SMC) will be consulted to review unblinded data to provide a recommendation on continuing enrollment. No formal statistical analyses are planned for this review.

## 4.4. Statistical Considerations for the Study Design

### 4.4.1. Sample Size Considerations

The safety, reactogenicity, and tolerability of the vaccine regimens are the primary endpoints for this study. The table below demonstrates effect size with a power of 80%, calculated at a variety of sample sizes.

Table S3 depicts SAE or AESI rates and associated 95% confidence intervals in each potential grouping of interest given 0-5 participants with observed events. If we were to observe zero events within a single active study group ( $n=20$ ), the upper limit of a 2-sided exact 95% CI would be 13.9% and true events above this could be ruled out at the  $\alpha=0.025$  level.

**Table S4: Exact 95% Clopper-Pearson CI for the SAE Rate in Each Study Group**

Number of Participants with Event	All Active Groups ( $n=60$ )	Any Active Group ( $n=20$ )
0	0% (0%, 4.9%)	0% (0%, 13.9%)
1	1.7% (<0.1%, 8.9%)	5.0% (0.1%, 24.9%)
2	3.3% (0.4%, 11.5%)	10.0% (1.2%, 31.7%)
3	5.0% (1.0%, 13.9%)	15.0% (3.2%, 37.9%)
4	6.7% (1.8%, 16.2%)	20.0% (5.7%, 43.7%)

Number of Participants with Event	All Active Groups (n=60)	Any Active Group (n=20)
5	8.3% (2.8%, 18.4%)	25.0% (8.7%, 49.1%)

Table S4 presents the estimated power for the secondary outcome of antibody titer based on the published data from Pitisuttithum P et.al. For the analysis of this experiment, we plan on observing a single measurement of peak antibody level per participant. Thus, the study is designed around a 1-way ANOVA model. Tukey's method will be used in the pairwise comparison test. In the analysis, we looked at the size of the error bars on the peak of the log antibody titer and based upon our visual inspection we assumed that the residual standard deviation is = 0.2. A sample size of approximately 20 participants per arm was selected to provide  $\geq 80\%$  power to detect the effect size of  $\geq 0.202$  between study arms. Statistical significance will be set at  $p \leq 0.05$ .

**Table S5: Sample size per arm and minimum effect size with 80% power, assuming residual standard deviation of 0.2**

Part A: 3 Active arms		
n per arm	Minimum effect size	Power
15	0.236	0.803
16	0.228	0.804
17	0.220	0.801
18	0.214	0.803
19	0.208	0.803
20	0.202	0.802

#### 4.4.2. Allocation of Participants to Study Arms (Randomization)

Randomization will be conducted using a modified permuted 1:1:1 randomization block scheme described in a separate randomization plan held by the protocol statistician. To maintain blinding of the sentinel group, four participants in the sentinel group will be randomized to the 200 mcg ALFQ group (Arm 1), and one participant each will be randomized to the 100 mcg ALFQ group (Arm 2) and 50 mcg ALFQ group (Arm 3). Thereafter, when the study continues enrollment, randomizations will be administered in such a way as to achieve the eventual 1:1:1 overall balance. Once a randomization number has been assigned, it will not be re-assigned. If a participant withdraws from the study or discontinues vaccination before all slots have been filled, the vacated randomization slot will be filled with the next available participant while enrollment is open. The randomization list will be uploaded into REDCap by the DCAC data manager and will be accessed by the unblinded site pharmacist(s). The protocol statistician will generate a final listing of all randomizations with vaccinations dates upon completion of the study and after

the database has been locked (Listing 1). Additional randomization details are provided in the randomization plan.

## 4.5. Study Products

### 4.5.1. Study Products Administered

The study products administered include the glycoprotein A244, the recombinant HIV-1 Env protein B.63521, and the ALFQ adjuvant.

### 4.5.2. Identity of Investigational Product(s)

A244 consists of the gp120 envelope glycoprotein HIV-1 subtype CRF\_01E A244 derived from the CM244 CRF\_01AE. The A244 gp120 envelope has an 11 amino N-terminal deletion, similar to the A244 protein used in AIDSVAX B/E.

B.63521 gp120 is a recombinant HIV-1 Env protein containing an 11 amino acid truncation at the N-terminus of gp120 that enhances antigenicity and immunogenicity.

ALFQ (Army Liposomal Formulation) is a liposomal adjuvant containing a synthetic monophosphoryl lipid A (MPLA) with the addition of QS-21 (protocol version 1, section 6.1).

### 4.5.3. Selection and Timing of Dose for Each Participant

This is a three-dose study, with participants receiving the assigned study product of interest at Month 0 (Day 1), Month 1 (Day 29), and Month 2 (Day 57).

### 4.5.4. Blinding

The PI, study staff, and participants will be blinded as to group allocation as it pertains to the dose of ALFQ. The unblinded pharmacy team will maintain all of the accountability logs and other product related regulatory documents, such as completed preparatory sheets. These documents will not be accessible to the blinded team. The unblinded pharmacy team will be in charge of emergency access to unblinding. In addition, the delegated unblinded study staff/nurse preparing the vaccine syringes will not be involved in the clinical assessment of participants and will be instructed not to comment on the appearance of experimental agent to study staff. For all participants, the volume of injection will be consistent. Procedures used for drug packaging and distribution to maintain blinding are described in the pharmacy manual and the clinical manual of procedures. To prevent a blinded person from seeing the IP in the syringe, the unblinded nurses will use blinding tape to prevent blinded study staff from looking at the viscosity and color of the product while in the syringe.

In a non-emergency event when a unexpected serious adverse reaction occurs that is suspected (i.e. possible/probably related) to the treatment, the study PI or designee will send an unblinding request to [rv575\\[contact]](mailto:[contact]), with ORA PSSO safety mailbox in copy, that includes the participant ID, reason for unblinding, and who should receive the unblinding information. The unblinded team at DCAC will provide the treatment assignment to the ORA PSSO representative within one business day of the request. Additional details are provided in the blinding management plan.

#### **4.5.5. Prior and Concomitant Therapy**

Concomitant medications will be recorded from 45 days prior to first vaccination until 10 months after the final vaccination. An initial review of past medical history will include a review of medications. Information pertaining to receipt of non-study vaccines, research agents, immunoglobulin preparations, immunosuppressive medication, antiretroviral drugs, and any blood products will be elicited at study visits and recorded in source documents.

To ensure appropriate medical follow-up for study participants, information regarding concomitant medications used in association with an AE will be collected and recorded in the source documents.

Otherwise, no other concomitant medication information will be collected.

#### **4.5.6. Study Product Compliance**

Any randomized participants who withdraw before receiving the study vaccination will be summarized in the participant disposition exhibits and reported in a listing. Those participants will be replaced by others determined to be eligible during screening visits.

### **4.6. Safety Variables**

Safety will be assessed both by direct physical examination and by diary cards, which serve as memory tools for better identification of reactions. Participants will be asked to record their temperature and complete a diary card at home in the evening after the vaccination and each day for the next 14 days. During vaccination visits on Day 1, 29, and 57, participants will be assessed for symptoms of local (at the injection site) reactogenicity prior to administration and 30 minutes post-administration: pain/tenderness, itching, warmth, induration, redness, and for symptoms of systemic reactogenicity: fever, myalgia, arthralgia, headache, fatigue, chills, nausea, dizziness, and rash. After review of the diary card and discussion with the participant, the study staff will document any post-vaccination reaction(s) and all related information (severity, frequency, etc.) concerning such a reaction in the participant's clinic source documents. The frequency and incidence of specific post-vaccination reactions and any reaction will be used for analysis.

AEs and SAEs will be recorded at all visits along with timing and possible attribution to Investigational Product. Because this clinical trial involves an adjuvant, AESIs will also be assessed. As with solicited events, the frequency and incidence of specific post-vaccination reactions and any reaction will be used for analysis.

Safety laboratory analyses of complete blood count, liver function tests, and pregnancy test in females will also be performed according to the SOE. In addition to abnormal findings reported as AEs, changes from baseline will be computed.

Vital signs (body temperature, pulse, respiratory rate, and blood pressure) will be measured both pre- and at 30 minutes post-vaccination.

### **4.7. Immunogenicity Variables**

Vaccine-induced immune responses will be assessed in study participants as detailed in the SOE.

Humoral responses will be assessed by HIV-specific binding antibody assays, HIV-specific neutralizing antibody assays, and non-neutralizing antibody function assays at baseline and days

1, 15, 29, 42, 57, 70, 168, and 336. Durability of IgG response will be assessed for each participant by estimating the decline in log10 IgG from peak to 6 and 12 months post final vaccination.

Measurement of CD4+ and CD8+ T-cell effector function will be evaluated through response by cytokines such as IFN- $\gamma$  and IL2. CD4+ lymphoproliferation will be measured with the CFSE assay. Innate immunity (e.g., NK cells) will be assessed by quantifying ADCC and ADCP, determining NK cell phenotype using various flow cytometric panels, cytokine array assays to characterize the type of cytokines elicited by this vaccine regimen with or without adjuvants, by the assessment of gene expression by DNA microarray and related techniques, and other related assays. B cell responses will be characterized in blood and in diverse anatomical compartments (provided by sigmoid biopsies and lymph nodes biopsies) in a subset of participants. Host gene transcription profile and signature to vaccine antigens will be assessed by RNA sequencing and related techniques.

#### **4.8. Other Variables**

Age, gender, sex at birth, place of birth, level of education, occupation, race/ethnicity, and baseline medical history of participants will be recorded. Participant disposition variables will include the numbers of participants in each group and overall completing visits and study assessments.

## 5. GENERAL STATISTICAL CONSIDERATIONS

### 5.1. General Principles

All continuous variables, with appropriate transformations (e.g., log, square root, or arcsin) applied as necessary, will be summarized using the following descriptive statistics: n (non-missing sample size), mean, standard deviation, median, minimum, and maximum. The frequency and percentages (with the non-missing sample size as the denominator) of observed levels will be reported for all categorical measures. Exact Clopper-Pearson confidence intervals will be computed for binary variables, where applicable. For continuous variables, confidence intervals will be computed based on the t-distribution with  $n-1$  degrees of freedom, where  $n$  denotes the number of observations. If the data are found to be non-normal, and the sample size is insufficient for application of the central limit theorem (which states that in sufficiently large samples, the sample mean is approximately normal), non-parametric bootstrapped confidence intervals may be calculated instead.

In general, all data listings will be sorted by treatment group and participant, and when appropriate by visit number within participant. All summary tables will be structured with a column for each treatment group in the order presented in the protocol and will be annotated with the total population size relevant to that table/treatment group, including any missing observations.

For hypothesis tests of continuous endpoints, an ANOVA will be preferred for global tests and t-tests will be preferred for pairwise tests. If histograms of the analysis data do not appear by visual inspection to be approximately normal, even after appropriate transformations, or if the sample sizes for comparisons groups are too small for the application of the central limit theorem, a Kruskal-Wallis test will be utilized instead of an ANOVA, and a Wilcoxon rank-sum test will be utilized instead of a t-test. For tests of categorical endpoints, a chi-square test or, if cell counts prohibit the use of a chi-square test, a Barnard's test or Fisher's exact test will be used as appropriate.

### 5.2. Timing of Analyses

The final study report will be completed when all primary objective data and secondary immunogenicity endpoint data are available. Additional exploratory immunogenicity analyses may be presented in separate reports and/or manuscripts, depending on data availability.

### 5.3. Analysis Populations

A tabular listing of all participants, visits, and observations excluded from the analysis populations will be provided in the final report. All data will be analysed based on intention-to-treat principles.

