9.5. Populations for Analyses

Analysis populations are defined in [Table 13](#).

Table 13: Analysis Populations

Population	Description
Enrolled	All participants who receive the first study vaccination
Randomized	All participants who are randomized to a study arm
Evaluable	All participants who receive the first study vaccination
Safety	All randomized participants who take at least 1 dose of study treatment. Participants will be analyzed according to the treatment they actually received
Immunogenicity	The immunogenicity population will include all participants who received at least one dose of vaccination and have at least one post-vaccination blood sample

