#### 5.3.1. Safety Population

All participants who received at least one dose of the vaccination and for whom any post-dose data is available will be included in the safety population.

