### 6.5. Measurements of Study Product Compliance

A listing presenting each participant's vaccination group and product received will be presented. Any participants who receive the wrong study vaccination and those who are randomized but not vaccinated will also be presented in a line listing.

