## 7. SAFETY EVALUATION

All summaries and analyses of safety data will be presented for the Safety Population. Safety summaries for the occurrence and severity of SAEs, AEs, AESIs, and unsolicited AES will be presented by vaccination group. The denominator for the percentages may be based on the number of non-missing observations for an assessment or based on the number of participants in a population. This will be described for each exhibit.

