**Listing 2: Discontinuations and Early Terminations**

Participant ID	Study Day of Discontinuation	Reason for Discontinuation	If Due to AE, AE Number	Terminated from Study?

Statistical Analysis Plan – RV575		Version 2.1	22 January 2024
Listing 3: Participants Not Receiving Assigned Study Vaccination			
Participant ID	Date of Enrollment	Assigned Study Group	Actual Study Group

**Listing 4:** Protocol Deviations

Participant ID (N/A if screening failure)	Study Group	Deviation Number	Deviation	Study Day
--	-------------	------------------	-----------	-----------

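### SAP 5.3 puts all data under intention-to-treat, which conflicts with the protocol's as-treated Safety population and leaves the dose grouping of a misdosed participant in the safety tables unsettled

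*SAP*

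**What the plan says.** Protocol 9.5, Table 13, defines the Safety population as randomized participants with at least one dose and adds a grouping rule: "Participants will be analyzed according to the treatment they actually received".

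The SAP handles the same matter in five places:

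- **SAP 5.3**, the opening of the section on analysis populations: "All data will be analysed based on intention-to-treat principles". Safety is not exempted.
- **SAP 5.3.1** gives an inclusion rule only: "All participants who received at least one dose of the vaccination and for whom any post-dose data is available". The protocol's grouping rule is absent.
- **SAP 7**: "All summaries and analyses of safety data will be presented for the Safety Population". The summaries "will be presented by vaccination group", a term that the SAP never defines as assigned or received.
- **SAP 6.5**: "Any participants who receive the wrong study vaccination and those who are randomized but not vaccinated will also be presented in a line listing". The shell for this is Listing 3, "Participants Not Receiving Assigned Study Vaccination", with columns for assigned and actual group.
- **SAP section 11** is reserved for substantial changes from the protocol's analysis plan. Its one entry, 11.1, concerns the interim immunogenicity analysis.

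**The concern.** The two documents give different grouping rules for the primary endpoint. The arms differ only in ALFQ dose (200, 100 or 50 µg), and the trial compares them to choose a dose. In that setting a reaction belongs with the dose that was injected. If it is tabulated under the assigned dose instead, the arms look more alike than they are, and a relation between dose and reactogenicity becomes harder to see.

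Listing 3 would make a misdosed participant visible to a reader. It would not move that participant's events between the columns of the safety tables or change a test. If the rule is left open, it would have to be chosen once the misdosed participant's results are known.

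**Working it through.** **Reading the passages together.** The documents state no figure on this point, so there is nothing to reproduce. The question is whether any SAP text restores the protocol's rule.

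1. The sentence in SAP 5.3 covers all data and heads the section that contains 5.3.1. Read literally, it applies to safety.
2. SAP 5.3.1 says who is in the population, not which column they go in.
3. SAP 7 relies on vaccination group. SAP 6.5 plans a listing that shows each participant's vaccination group and, as a separate item, the product received. This suggests that the group means the assigned arm, but does not define it.
4. The note under the Table 9 shell (solicited events by maximum severity) describes N in terms of having received the specified dose. Dose there could mean the ALFQ dose in the column heading or the dose number in the series. It is too ambiguous to override SAP 5.3.
5. SAP section 11 lists no change to the safety grouping.

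**Size of the effect.** Inputs: 20 per arm (Protocol 4.1). Assumption: one participant assigned to one arm receives another arm's product and reacts. The documents give no misdosing rate.

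Let x be the reactors in the assigned arm, counting this participant, and y the reactors among the 20 assigned to the arm whose product was received.

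- Assigned arm: x/20 by assignment, (x − 1)/19 by receipt. Difference = (20 − x)/380.
- Receiving arm: y/20 by assignment, (y + 1)/21 by receipt. Difference = (20 − y)/420.

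| Case | By assignment | By receipt | Shift |
|---|---|---|---|
| Assigned arm, x = 1 | 1/20 = 5.0% | 0/19 = 0% | 19/380 = 5.0 points |
| Assigned arm, x = 12 | 12/20 = 60.0% | 11/19 = 57.9% | 8/380 = 2.1 points |
| Receiving arm, y = 0 | 0/20 = 0% | 1/21 = 4.8% | 20/420 = 4.8 points |

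For a misdosed participant who does not react, the shifts are x/380 and y/420, with the same ceilings (19/380 = 5.0 points and 20/420 = 4.8 points). So 5 points is the maximum for one arm. When one arm falls and the other rises, the contrast between them can move by up to 5.0 + 4.8 = 9.8 points.

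Exact 95% Clopper-Pearson intervals for a single event, in a participant assigned 50 µg who received 200 µg:

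- By assignment: 50 µg 1/20 (0.1% to 24.9%); 200 µg 0/20 (0% to 16.8%).
- By receipt: 50 µg 0/19 (0% to 17.6%); 200 µg 1/21 (0.1% to 23.8%).

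**Can it change a test?** Protocol 9.6.2 allows pairwise comparisons at two-sided 0.05. Two-sided Fisher tests for the same misdosed reactor, with invented counts for everyone else:

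| Other reactors, 200 µg / 50 µg | By assignment | By receipt |
|---|---|---|
| 5 / 0 | 5/20 vs 1/20, p = 0.18 | 6/21 vs 0/19, p = 0.021 |
| 6 / 0 | 6/20 vs 1/20, p = 0.091 | 7/21 vs 0/19, p = 0.009 |
| 5 / 1 | 5/20 vs 2/20, p = 0.41 | 6/21 vs 1/19, p = 0.095 |

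A single error can cross 0.05 in the first two patterns and does not in the third.

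**The case against.** The best defence is that SAP 5.3 is loose wording, not a decision. The SAP's preface says that it expands on the protocol, and section 11 announces no change, so Table 13 may simply still govern. The subsections under 5.3 already depart from strict intention-to-treat by requiring a dose, requiring data, or allowing per-protocol exclusions. The Table 9 note can be read as counting by dose received. This has force: a reader might infer that the SAP deliberately replaced the as-treated rule, or that its tables are certain to miscount, and the documents support neither. But the only grouping principle that the SAP states is the one in 5.3, and a programmer following it would use the assigned arm. The defence supports clarifying the text, not leaving it.

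A reader might also infer from Listing 3 that wrong-dose administration is expected or has happened. It does not show that. The same sentence in SAP 6.5 covers people randomized but never vaccinated. Some shells are generic: Table 4 has an infusion category in an intramuscular vaccine trial. The SAP revision history mentions out-of-window vaccinations but no wrong-dose event. A designated unblinded nurse prepares the product on the day (Protocol 6.2.3), and every administration is documented (Protocol 6.3).

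Finally, 5 points is a ceiling, reached when events are rare. Protocol 2.2.3 cites at least one mild solicited event in 58.3% of one arm of an earlier study at 200 µg ALFQ, and at rates like that the shift is nearer 2 points. This stands.

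**Conclusion.** The contradiction is real and concerns the primary endpoint. Protocol Table 13 groups safety by treatment received, SAP 5.3 literally groups all data by assignment, and nothing else in the SAP resolves it.

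The consequence is conditional. It needs at least one participant to receive an ALFQ dose other than the one assigned, and the documents report none. Without such a case the two rules agree and no result changes. With one case, an arm's proportion moves by at most about 5 percentage points, assuming 20 per arm. The reversed p-values above rest on invented counts: they show that a conclusion could change, not that it would.

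Copying Table 13 into the SAP would not be enough. Each participant has three vaccinations, and Table 13 does not say where someone misdosed at only one of them belongs. The point merits correction because the rule should be fixed before anyone sees results by arm.

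**What to change.** Before unblinding, which is when SAP section 11 already promises a review and update:

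1. In SAP 5.3, limit the intention-to-treat sentence to immunogenicity.
2. In SAP 5.3.1, state that safety is analysed by the ALFQ dose actually received, as in protocol Table 13.
3. Define vaccination group accordingly for the safety tables, and reword the Table 9 note so that dose has one meaning.
4. Add an analysis rule for participants who receive different doses at different vaccinations. For example, attribute solicited events to the dose received at that vaccination, and state in advance one grouping for whole-study summaries.

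If the sponsor does want safety grouped by assignment, it should record and justify that in section 11 as a departure from Table 13.

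The cost is a few SAP sentences. Trial conduct, data collection and sample size are unaffected.
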